Protocol Synopsis Title

A Phase II study, randomized, controlled, efficacy assessor blinded, multi-center, international prospective study to assess the safety and effectiveness of Medi-Tate i-Temporary Implantable Nitinol Device (iTIND) in subjects with symptomatic Benign Prostatic Hyperplasia (BPH)

Protocol Date
10 May 2015
Protocol Number
MT-03
Protocol Version
Version 6

NCT02506465

Synopsis

TITLE: A Phase II, randomized, controlled, efficacy assessor blinded, multi-center, international prospective study to assess the safety and effectiveness of Medi-Tate i-Temporary Implantable Nitinol Device (iTIND) in subjects with symptomatic Benign Prostatic Hyperplasia (BPH)

PROTOCOL NUMBER: MT-03

INVESTIGATIONAL PRODUCT: Medi-Tate i-Temporary Implantable Nitinol Device (iTIND)

PHASE: II

INDICATION: Subjects with symptomatic BPH

STUDY OBJECTIVES: The study objectives are to demonstrate the efficacy and safety of the Medi-Tate iTIND as compared to control group (catheter only).

Population: Up to 190 subjects may be enrolled in the study in order to obtain a sample population of 170 randomized subjects with symptomatic BPH.

INCLUSION AND EXCLUSION CRITERIA

Inclusion Criteria:

Subjects must meet all of the inclusion criteria listed below to be eligible for randomization into the study:

- 1. Subject signed informed consent form (ICF)
- 2. Age 50 and above
- 3. Male with symptomatic BPH.
- 4. IPSS symptom severity score ≥ 10
- 5. Peak urinary flow of < 12 ml/sec. Meeting the criterion on (2) two separate voiding trials, on a minimum voided volume of at least 125 cc for each voiding trial.
- 6. Prostate volume between 25 ml to 75 ml (assessed by ultrasound)
- 7. Blood CBC and biochemistry up to two weeks before screening demonstrating: Normal values of the PT, PTT and INR tests (anticoagulants should be stopped according to GCP)
- 8. Subject able to comply with the study protocol
- 9. Normal Urinalysis and urine culture

Exclusion Criteria:

Subjects with any one of the exclusion criteria listed below will not be eligible for randomization into the study:

- 10. Cardiac arrhythmias, cardiac disease including congestive heart failure, uncontrolled diabetes mellitus, significant respiratory disease, or known immunosuppression;
- 11. Neurogenic bladder and/or sphincter abnormalities due to Parkinson's disease, multiple sclerosis, cerebral vascular accident, diabetes
- 12. A post void residual (PVR) volume > 250 ml measured by ultrasound or acute urinary retention
- 13. Compromised renal function (i.e., serum creatinine level > 1.8 mg/dl, or upper tract

disease);

- 14. Confirmed or suspected bladder cancer;
- 15. Recent (within 3 months) cystolithiasis or hematuria;
- 16. Urethral strictures, bladder neck contracture, urinary bladder stones or other potentially confounding bladder pathology;
- 17. An active urinary tract infection.
- 18. Enrolled in another treatment trial for any disease within the past 30 days.
- 19. Previous colo- rectal surgery (other than hemorrhoidectomy) or history of rectal disease if the therapy may potentially cause injury to sites of previous rectal surgery, e.g., if a transrectal probe is used;
- 20. Previous pelvic irradiation, cryosurgery or radical pelvic surgery;
- 21. Previous prostate surgery, balloon dilatation, stent implantation, laser prostatectomy, hyperthermia, or any other invasive treatment to the prostate
- 22. History of prostatitis within the past 5 years.
- 23. Median lobe obstruction of the prostate.
- 24. Cancer that is not considered cured, except basal cell or squamous cell carcinoma of the skin (cured defined as no evidence of cancer within the past 5 years).
- 25. Any serious medical condition likely to impede successful completion of the study
- 26. Participating in any other investigational study for either drug or device which can influence collection of valid data under this study.
- 27. Subjects who are actively taking medications that affects urination and BPH symptoms not completing the required washout period.
- 28. Baseline PSA \geq 10 ng/ml.
- 29. Positive DRE.
- 30. Baseline PSA between 2.5–10 ng/ml and free PSA < 25%, without a subsequent negative prostate biopsy.

For clarification, a subject with a baseline PSA < 2.5 ng/ml or a subject with a baseline PSA between 2.5-10 ng/ml and free PSA $\ge 25\%$ will not require additional testing and may be enrolled if the remaining inclusion/exclusion criteria are satisfied.

Intraoperative Exclusion Criteria:

31. Any abnormal findings on cystoscopy at the time of implantation (iTIND group) that would be inconsistent with the diagnosis of BPH.

STUDY DESIGN, DURATION AND PROCEDURES:

Up to 190 subjects will be enrolled in the study in order to obtain a sample population of 170 randomized subjects.

Study duration is 12 months and includes 7 visits.

DEVICE/TREATMENT AND ROUTE OF ADMINISTRATION:

iTIND Device will be implanted for 5-7 days. Sham will be a routine Foley catheter placement and removal procedure conducted at the implantation visit and at the device retrieval visit.

SAFETY VARIABLES:

- Incidence (% of patients) and frequency (no. of events) of device related adverse events
- Incidence (% of patients) and frequency (no. of events) of any adverse events
- Safety laboratory measurements
- Vital signs and physical examinations

EFFICACY VARIABLES:

Primary Endpoint:

The primary efficacy endpoints for this study are:

- Change from baseline to month 3 in the IPSS/ AUA-SI Score. Analysis will compare the differences between the two study groups.
- Change from baseline to month 12 in the IPSS/ AUA-SI Score. Analysis will assess the within iTIND group change.

Secondary Endpoints:

Analysis will compare the differences between groups in:

- Change from baseline to month 3 in IIEF (International Index of Erectile Function),
- Change from baseline to month 3 in SHIM (Sexual Health Inventory for Men)
- Change from baseline to month 3 in Qmax (maximum urinary flow rate)
- Change from baseline to month 3 in PVR (post-void residual urine volume),

STATISTICAL METHODOLOGY:

A total of 170 subjects randomized to treatment with either iTIND arm or to the control arm using a respective randomization scheme of 2:1 are expected to be recruited into this trial. Since it is anticipated that some of the participating sites will recruit an insufficient number of subjects to allow estimation of within sites effect size or treatment by site interaction study centers will be pooled into Country/Geographical Region (CGR).

Randomization:

Subjects will be randomized using a 2:1 assignment ratio to either iTIND group or to the control group, respectively. Randomization will employ permuted blocks stratified by center.

Overall Significance Level:

The overall significance level for this study will be 5% using two-tailed tests. To preserve the overall type-I error of the study the following will take place:

- The study identifies two primary endpoints and four secondary end-points ordered in a hierarchy.
- Meeting both primary endpoints at type-I error of 5% each, is sufficient to determine study success in demonstrating the effectiveness and effect durability of iTIND treatment.
- Secondary endpoints will be tested only if both primary endpoints are met.
- Type-I error control for multiple endpoints testing will utilize the gate keeping approach performed according to the following hierarchy order:

- 1. Change from baseline to month 3 in IIEF (International Index of Erectile Function)
- 2. Change from baseline to month 3 in SHIM (Sexual Health Inventory for Men)
- 3. Change from baseline to month 3 in Qmax (maximum urinary flow rate)
- 4. Change from baseline to month 3 in PVR (post-void residual urine volume)

Sample Size Rationale

Study power was estimated for both primary endpoints to ensure that study is adequately powered to meet both endpoints.

The first primary endpoint for this study is the change from baseline to month 3 in the IPSS/AUA-SI score and analysis is planned to compare the changes of both study arm. The power of the trial for this endpoint was estimated based the following assumptions for that primary endpoint:

- The expected STD of the 3-month change from baseline for the 2 study arm is 7.35 IPSS/AUA-SI points.
- The expected effect size (difference between the changes in the iTIND arm and the control arm) is 4 IPSS/ AUA-SI points.
- A two-sample t-test employing a 5% two-tailed testing was used to estimate study power.
- Analysis suggested that for an expected effect size of 4 IPSS/ AUA-SI points, STD of change of 7.35 IPSS/ AUA-SI points, using a 5% two-tailed testing, a total of 170 subjects randomized to either iTIND group or the control using a respective randomization scheme of 2:1 will provide a power of 87.7% for this endpoint.

The second primary endpoint for this study is the change from baseline to month 12 in the IPSS/AUA-SI score and analysis will assess the within iTIND group change. The power of the trial for this endpoint was estimated based the following assumptions:

- The expected mean 12-month change and STD of the 12-month change from baseline for the iTIND arm are 4.0 and 7.35 IPSS/ AUA-SI points, respectively.
- Endpoint will be met if the lower bound of the two-sided 95% confidence interval for that 12-month mean change from baseline calculated for the iTIND arm will be higher than 1 IPSS/AUA-SI point reflecting a 25% boundary as compared to the expected mean effect size (4.0 IPSS/AUA-SI points).
- A two-sided 95% confidence interval for the 12-month change from baseline within the iTIND arm was used to estimate study power.
- Analysis suggested that for the 12-month change analysis of the iTIND arm a total of 100 subjects will provide a power of 97.8% for this endpoint.

Principal Analysis of the Two Primary Endpoints

- Subjects prescribed with alpha blockers or with 5-ARIs following initiation of study treatment and up to the period that ends at 12-month follow-up visit will be considered, for the purpose of statistical analysis, as treatment failures starting from the date in which these medications were administered. To account for this potential source of bias in the analysis, all IPSS/AUA-SI measurements of an individual subject, starting from the date of initiation of alpha blockers or 5-ARIs administration will be imputed to be their baseline values.
- The principle analysis of the two primary endpoints will be performed for the ITT analysis

set. The statistical model to be used for inference of the two primary endpoints will be a repeated measures model (SAS® MIXED procedure with REPEATED sub-command). The model will include the following fixed effects: categorical month in trial by treatment interaction and baseline IPSS/AUA-SI measurement as one degree of freedom covariate. The unstructured covariance matrix for repeated observations within subjects will be used. In case that the model will not converge, the Maximum-Likelihood (ML) estimation method will be used instead of the default Restricted ML (REML). If the model still does not converge then a simpler covariance structures with less parameters will be used, according to the following order: Heterogeneous Autoregressive(1) (ARH(1)), Heterogeneous Compound Symmetry (CSH), Autoregressive(1) (AR(1)), and Compound Symmetry (CS).

- The Least Square Means (LSM) at Month 3 visit of the change from baseline will be compared between the iTIND arm and the control group and will be used for inference regarding the first primary endpoint.
- The Least Square Means (LSM) at Month 12 visit of the change from baseline within the iTIND arm will be used for inference regarding the second primary endpoint. In the case that the Lower CI of the Least Squares Means SAS table will be higher than 1 IPSS/ AUA-SI score point then a positive inference will be made regarding the second primary endpoint.
- Study will be considered positive if both primary endpoints are met.
- To assess the robustness of results and conclusions and the potential impact of missing values a comprehensive set of sensitivity analysis will be performed.

Statistical Analysis Plan (SAP)

The study will be conducted when the Sponsor and the Biostatistician assigned to the study are fully blinded to treatment assignment. A more detailed SAP will be developed by the statistician prior to revealing of the study blind.

I. STATISTICAL METHODOLOGY

A total of 170 subjects randomized to treatment with either iTIND arm or to the control arm using a respective randomization scheme of 2:1 are expected to be recruited into this trial. Since it is anticipated that some of the participating sites will recruit an insufficient number of subjects to allow estimation of within sites effect size or treatment by site interaction study centers will be pooled into Country/Geographical Region (CGR).

A. RANDOMIZATION PROCEDURE

Subjects will be randomized using a 2:1 assignment ratio to either iTIND group or to the control group, respectively. Randomization will employ permuted blocks stratified by center.

B. SAMPLE SIZE RATIONALE

Study power was estimated for both primary endpoints to ensure that study is adequately powered to meet both endpoints.

The first primary endpoint for this study is the change from baseline to month 3 in the IPSS/AUA-SI score and analysis is planned to compare the changes of both study arms. The power of the trial for this endpoint was estimated based the following assumptions for that primary endpoint:

- The expected STD of the 3-month change from baseline for the 2 study arm is 7.35 IPSS/AUA-SI points.
- The expected effect size (difference between the changes in the iTIND arm and the control arm) is 4 IPSS/ AUA-SI points.
- A two-sample t-test employing a 5% two-tailed testing was used to estimate study power.
- Analysis suggested that for an expected effect size of 4 IPSS/ AUA-SI points, STD of change of 7.35 IPSS/ AUA-SI points, using a 5% two-tailed testing, a total of 170 subjects randomized to either iTIND group or the control using a respective randomization scheme of 2:1 will provide a power of 87.7% for this endpoint.

The second primary endpoint for this study is the change from baseline to month 12 in the IPSS/AUA-SI score and analysis will assess the within iTIND group change. The power of the trial for this endpoint was estimated based the following assumptions for that primary end-point:

- The expected mean 12-month change and STD of the 12-month change from baseline for the iTIND arm are 4.0 and 7.35 IPSS/ AUA-SI points, respectively.
- Endpoint will be met if the lower bound of the two-sided 95% confidence interval for that 12-month mean change from baseline calculated for the iTIND arm will be higher than 1

IPSS/ AUA-SI point reflecting a 25% boundary as compared to the expected mean effect size (4.0 IPSS/AUA-SI points).

- A two-sided 95% confidence interval for the 12-month change from baseline within the iTIND arm was used to estimate study power.
- Analysis suggested that for the 12-month change analysis of the iTIND arm a total of 100 subjects will provide a power of 97.8% for this endpoint.

C. OVERALL SIGNIFICANCE LEVEL

The overall significance level for this study will be 5% using two-tailed tests. To preserve the overall type-I error of the study the following will take place:

- The study identifies two primary endpoints and four secondary end-points ordered in a hierarchy.
- Meeting both primary endpoints at type-I error of 5% each, is sufficient to determine study success in demonstrating the effectiveness and effect durability of iTIND treatment.
- Secondary endpoints will be tested only if both primary endpoints are met.
- Type-I error control for multiple endpoints testing will utilize the gate keeping approach performed according to the following hierarchy order:
 - 1. Change from baseline to month 3 in IIEF (International Index of Erectile Function)
 - 2. Change from baseline to month 3 in SHIM (Sexual Health Inventory for Men)
 - 3. Change from baseline to month 3 in Qmax (maximum urinary flow rate)
 - 4. Change from baseline to month 3 in PVR (post-void residual urine volume)

D. EFFICACY ENDPOINTS AND ANALYSES

The study identifies two primary endpoints and four secondary end-points ordered in a hierarchy for significance testing as provided below.

a. Primary Endpoints

The two primary efficacy endpoints for this study which are given in the hierarchy order of significance testing for are:

- 1. Change from baseline to month 3 in the IPSS/ AUA-SI Score. Analysis will compare the differences between the two study groups.
- 2. Change from baseline to month 12 in the IPSS/ AUA-SI Score. Analysis will assess the within iTIND group change.

b. Secondary Endpoints

Secondary endpoints will be tested only if both primary endpoints are met. Analysis will compare the differences between groups at month 3 and significance testing will be performed, utilize the gate keeping approach, according to the hierarchy order outlined below:

- 1. Change from baseline to month 3 in IIEF (International Index of Erectile Function),
- 2. Change from baseline to month 3 in SHIM (Sexual Health Inventory for Men)
- 3. Change from baseline to month 3 in Qmax (maximum urinary flow rate)
- 4. Change from baseline to month 3 in PVR (post-void residual urine volume),

E. ANALYSIS SETS

a. Intent-to-Treat (ITT) Analysis Set

The intent-to-treat (ITT) population will include all randomized patients according to treatment subjects were randomized to regardless of treatment they actually received.

b. Safety (ST) Analysis Set

The safety population will include all randomized patients who initiated study treatment procedures according to treatment actually administered.

c. 3-Months Completer Analysis Set (CO3M)

The 3-Month completer analysis set (CO_{3M}) will consist of all subjects who complete the 3 months comparative phase of the study.

Note: Subjects who are excluded intra-operatively due to abnormal findings on cystoscopy will not be included in the analysis populations outlined above. Any such exclusions will be reported, including demographics, baseline characteristics and reasons for exclusion.

F. DEMOGRAPHIC BASELINE CHARACTERISTICS ANALYSIS

Demographic and baseline data will be performed for the ITT analysis set. Subject demographic and baseline characteristics, including BPH prognostic factors will be examined to assess the comparability of the treatment groups. Medical history, Prior medications, will be summarized using descriptive statistics. For continuous variables, descriptive statistics (number [n], mean, standard deviation, standard error, median, minimum, and maximum) will be provided. For

categorical variables, subject counts and percentages will be provided. Categories for missing data will be presented if necessary.

G. PLANNED METHOD OF ANALYSIS

All formal pre-defined significance testing will be performed for the ITT Analysis Set.

- a. Principal Analysis of the Two Primary Endpoints
- Subjects prescribed with alpha blockers or with 5-ARIs following initiation of study treatment and up to the period that ends at 12-month follow-up visit will be considered, for the purpose of statistical analysis, as treatment failures starting from the date in which these medications were administered. To account for this potential source of bias in the analysis, all IPSS/AUA-SI measurements of an individual subject, starting from the date of initiation of alpha blockers or 5-ARIs administration will be imputed to be their baseline values.
- The statistical model to be used for inference of the two primary endpoints will be a repeated measures model (SAS® MIXED procedure with REPEATED sub-command). The model will include the following fixed effects: categorical month in trial by treatment interaction and baseline IPSS/AUA-SI measurement as one degree of freedom covariate. The unstructured covariance matrix for repeated observations within subjects will be used. In case that the model will not converge, the Maximum-Likelihood (ML) estimation method will be used instead of the default Restricted ML (REML). If the model still does not converge then a simpler covariance structures with less parameters will be used, according to the following order: Heterogeneous Autoregressive(1) (ARH(1)), Heterogeneous Compound Symmetry (CSH), Autoregressive(1) (AR(1)), and Compound Symmetry (CS).
- The Least Square Means (LSM) at Month 3 visit of the change from baseline will be compared between the iTIND arm and the control group and will be used for inference regarding the first primary endpoint.
- The Least Square Means (LSM) at Month 12 visit of the change from baseline within the iTIND arm will be used for inference regarding the second primary endpoint. In the case that the Lower CI of the Least Squares Means SAS table will be higher than 1 IPSS/ AUA-SI score point then a positive inference will be made regarding the second primary endpoint.
- Study will be considered positive if both primary endpoints are met.
 - b. Sensitivity Analysis of the Two Primary Endpoints
 - i. Types Of Missing Values

Before revealing of the blind, missing observations will be classified according to the following three types of missing values which are defined according to the relation of the missingness mechanism to observed and unobserved data:

- Missing Completely At Random (MCAR): If the missing value reason deemed unrelated to the observed or to the unobserved IPSS/AUA-SI score

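### The 87.7% month-3 power claimed for 170 subjects at 2:1 does not follow from the stated inputs, which give about 91.5%; the number of subjects behind 87.7% is not stated

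*Combined protocol and SAP*

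**What the plan says.** The sample size rationale appears twice in the same terms, in the synopsis and in SAP section B. For the month-3 comparison it gives all the inputs to a power calculation:

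- Difference: "The expected effect size (difference between the changes in the iTIND arm and the control arm) is 4 IPSS/ AUA-SI points".
- Standard deviation: "The expected STD of the 3-month change from baseline for the 2 study arm is 7.35 IPSS/AUA-SI points".
- Test: "A two-sample t-test employing a 5% two-tailed testing was used to estimate study power".
- Allocation (SAP section A): "Subjects will be randomized using a 2:1 assignment ratio to either iTIND group or to the control group, respectively".
- Size and result: "170 subjects randomized to either iTIND group or the control using a respective randomization scheme of 2:1 will provide a power of 87.7" percent.

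For the second primary endpoint, the within-iTIND change at month 12, the rationale uses a different number: "for the 12-month change analysis of the iTIND arm a total of 100 subjects will provide a power of 97.8% for this endpoint".

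The one numerical allowance for loss of subjects is in the synopsis under study design: "Up to 190 subjects will be enrolled in the study in order to obtain a sample population of 170 randomized subjects". That allowance is used up before randomization.

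**The concern.** The sentence ties one power figure to one design, and every quantity needed to check it is given. A gap of nearly four points is too large to be rounding, so either an input or the number of subjects used differs from what is written.

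The document also uses 100 iTIND subjects at month 12, whereas 170 at 2:1 implies about 113. Nothing connects the two numbers. If the month-3 power was worked out on a reduced, evaluable number, that number is the trial's retention target and it is missing. A reader then cannot tell how many subjects per arm the claim rests on, or whether the follow-up achieved meets the plan.

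**Working it through.** **Inputs** (synopsis and SAP section B): difference δ = 4; standard deviation σ = 7.35 in both arms; two-sided α = 0.05; total 170 at 2:1. Since 170 × 2/3 = 113.3, the nearest whole-number split is 113 iTIND and 57 control.

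**Formula.** For a two-sample t-test with n₁ and n₂ subjects:

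- standard error SE = σ √(1/n₁ + 1/n₂)
- noncentrality λ = δ / SE
- power = P(|T| > t₀.₉₇₅), where T is noncentral t with n₁ + n₂ − 2 degrees of freedom and noncentrality λ

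**Step 1. Try to reproduce 87.7% with 170 subjects.**

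SE = 7.35 × √(1/113 + 1/57) = 1.194; λ = 4 / 1.194 = 3.350; t₀.₉₇₅ on 168 df = 1.974; power = 91.48%.

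| Split of 170 | Power |
|---|---|
| 113 / 57 | 91.48% |
| 114 / 56 | 91.24% |
| 112 / 58 | 91.70% |

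The normal approximation at 113/57 gives Φ(3.350 − 1.960) = 91.77%, which is further from 87.7%. The choice of method therefore does not explain the gap. The difference is 91.5 − 87.7 = 3.8 points, or 91.2 − 87.7 = 3.5 points with 114/56.

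**Step 2. What would have to change to get 87.7%?**

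- Keeping 113/57 and δ = 4, the standard deviation would have to be about 7.85, not 7.35.
- Keeping 113/57 and σ = 7.35, the difference would have to be about 3.75, not 4.
- Keeping 170 in total, the split would have to lie between 124/46 (87.99%) and 125/45 (87.55%), about 2.7:1 and not 2:1.
- Keeping 170 at 2:1 but testing at two-sided 2.5% gives 86.1%, which neither matches 87.7% nor agrees with the stated 5%.

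**Step 3. Which number of subjects gives 87.7%?**

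At 100/50: SE = 7.35 × √(1/100 + 1/50) = 1.273; λ = 3.142; t₀.₉₇₅ on 148 df = 1.976; power = 87.73%.

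The neighbouring totals at the nearest whole-number split miss: 99/50 gives 87.6% and 101/50 gives 87.8%. At 2:1, 150 is therefore the only total that rounds to 87.7%. Against 170 that is a loss of 1 − 150/170 = 11.8%.

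Splits away from 2:1 also fit: 104/49 gives 87.71%, 96/51 gives 87.70% and 90/53 gives 87.73%. The match at 100/50 does not prove that 100/50 was used.

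**Step 4. Cross-check with the month-12 calculation.** The expected change is 4.0 and the lower confidence limit must exceed 1, so the distance to detect is 3 with σ = 7.35. A one-sample noncentral t with n = 100 gives λ = 3 / (7.35/√100) = 4.082 and power 98.1%, close to the stated 97.8%. With n = 113 it would be 99.0%. The 100 is thus broadly consistent with its own power figure, and it is fewer than 170 at 2:1 supplies.

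**Step 5. Do the stated allowances close the gap?** The step from 190 enrolled to 170 randomized is 1 − 170/190 = 10.5%, but it precedes randomization and leaves 170 unchanged. Removing subjects from the iTIND arm alone, down to 100 against 57 controls, gives 90.3%, still well above 87.7%.

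**The case against.** The strongest reply is that 87.7% already allows for dropout and that the trial is, if anything, better powered than claimed. The plan does expect subjects to be lost after assignment. Exclusion criterion 31 acts at implantation in the iTIND group, the note in SAP section E removes those subjects from every analysis set, and SAP section G classifies missing observations by type. This stands in part: such loss is foreseen. But no rate or evaluable number is attached to it, and the sentence attributes its power to 170 randomized subjects.

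A second objection is that the 100/50 reconstruction is weakly supported. The 100 belongs to month 12, not month 3; using it at both visits would imply no loss in between; and 97.8% is not an exact match at n = 100 (98.1%). Loss confined to the iTIND arm would not leave a 2:1 split either. All of this is fair, and 100/50 should be treated as a possibility only. The discrepancy does not depend on it.

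Third, 91.5% is not the trial's power either. The principal analysis is a baseline-adjusted repeated measures model in which scores after alpha-blocker or 5-ARI use are set back to baseline. That is correct: 91.5% is what the stated t-test inputs give with complete follow-up, and it should carry that qualification.

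Finally, the more detailed SAP that the plan promises may give the evaluable number. It would not correct the sentence as it stands here.

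**Conclusion.** The stated power is wrong as written. With the plan's own difference, standard deviation, test, alpha and allocation, 170 subjects give 91.5% (113/57) or 91.2% (114/56), not 87.7%. These figures assume equal standard deviations in the two arms and no loss after randomization. The number of subjects that underlies 87.7% is not stated; 150 at 2:1 fits, which would mean about 11.8% loss, but that is inferred.

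This is a minor point. The error understates the power of the design as described, so it gives no reason to think the trial too small. Sample size, alpha, analysis and success rule all stand. What is missing is a traceable basis for a primary-endpoint power claim, and a link between the roughly 113 iTIND subjects randomized and the 100 used at month 12.

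**What to change.** Amend the sample size rationale in both the synopsis and SAP section B:

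1. State that 170 subjects randomized 2:1 give about 91.5% power for the month-3 comparison under the listed assumptions with no loss.
2. State the evaluable number in each arm at month 3, and the loss from 170 that it implies, on which 87.7% rests. If the original calculation used 100 iTIND and 50 control subjects, say that 150 evaluable subjects give 87.7%. If it used something else, give that instead.
3. State whether the 100 iTIND subjects at month 12 reflect the same loss assumption.

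The sponsor's statistician should confirm the basis from the original calculation and not adopt the 100/50 reconstruction by default. The cost is a few sentences in two places, with no change to enrolment, alpha or analysis.

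### The Note in SAP I.E removes men excluded at cystoscopy, a rule stated for the iTIND group only, from the ITT set and every other analysis set

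*Combined protocol and SAP*

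**What the plan says.** SAP I.E.a defines the ITT set as "all randomized patients according to treatment subjects were randomized to regardless of treatment they actually received". SAP I.E.b defines the Safety set as "all randomized patients who initiated study treatment procedures according to treatment actually administered". I.E.c adds a 3-month completer set. The Note under these three definitions then says: "Subjects who are excluded intra-operatively due to abnormal findings on cystoscopy will not be included in the analysis populations outlined above". It continues: "Any such exclusions will be reported, including demographics, baseline characteristics and reasons for exclusion".

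The exclusion itself is criterion 31 in the Synopsis, listed under its own intraoperative heading: "Any abnormal findings on cystoscopy at the time of implantation (iTIND group) that would be inconsistent with the diagnosis of BPH". For the control arm, the Synopsis says: "Sham will be a routine Foley catheter placement and removal procedure conducted at the implantation visit and at the device retrieval visit". No cystoscopy and no matching exclusion are described for control.

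SAP I.G makes the ITT set the basis of inference: "All formal pre-defined significance testing will be performed for the ITT Analysis Set". The only comparison between analysis sets (SAP I.G.b.iv) is ITT against the 3-month completers.

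**The concern.** The ITT definition and the Note cannot both hold once a randomized man is excluded at cystoscopy. Two statisticians working from this SAP could build different ITT datasets.

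The exclusion also works on one side only. An iTIND subject with an unexpected finding is removed. A control subject with the same finding would not be examined for it, on the text available, and stays in. The arms then differ through selection made after assignment, which can bias the comparison in either direction. At stake are the month-3 comparisons for the first primary endpoint and the four secondary endpoints.

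For safety the harm is conditional. A man in whom the procedure had begun could meet the Safety definition and still be dropped by the Note. However, the SAP does not define when study treatment procedures are initiated. SAP I.H.a names no analysis set for adverse events and lists serious events case by case.

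**Working it through.** **Does the exclusion follow randomization?** No visit schedule is shown, so this is an inference, but a strong one.
- Criteria 1 to 30 govern eligibility for randomization; criterion 31 stands apart from them.
- A rule confined to the iTIND group at implantation presupposes a known assignment.
- The sham catheter is placed at the same visit.
- The Note is needed only if these men would otherwise be in a set of randomized patients.

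**Does another planned analysis recover these men?** No. The Note reduces both ITT and the completer set, so comparing the two cannot show its effect. The zero-change analysis in SAP I.G.b.iii is not stated to reach subjects outside the analysis sets.

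**The plan's own power figures.** Inputs from SAP I.B: difference 4, SD 7.35, two-sided 5%, 170 subjects at 2:1 (about 113:57). A noncentral-t calculation gives 91.5% at 113:57. The stated 87.7% is reproduced at 100:50. For month 12, n = 100, mean 4 and a bound of 1 give 98.1% against the stated 97.8%. The month-3 mismatch is a separate matter and does not bear on this point.

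**Illustrative bias with the Note in force.** The exclusion rate p and the gap g are assumptions. The gap is the number of points by which excluded men would have improved less (+) or more (-) than the remaining iTIND men. With no true effect:
- bias = p × g
- SE = 7.35 × √(1/[113(1 - p)] + 1/57), which is 1.198, 1.205 and 1.216 at p = 2%, 5% and 10%
- error rates come from the noncentral t with noncentrality bias/SE

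| Excluded | Men | Bias, gap ±2 | Two-sided error | Bias, gap ±4 | Two-sided error | False iTIND win, gap +4 | False iTIND win, gap -4 |
|---|---|---|---|---|---|---|---|
| 2% | about 2 | 0.04 | 5.01% | 0.08 | 5.05% | 2.9% | 2.1% |
| 5% | about 6 | 0.10 | 5.08% | 0.20 | 5.3% | 3.6% | 1.7% |
| 10% | about 11 | 0.20 | 5.3% | 0.40 | 6.2% | 5.1% | 1.1% |

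Bias is in IPSS points and takes the sign of the gap; a positive value favours iTIND. The nominal false-win rate is 2.5%, and a gap of zero gives no bias. A gap of 4 equals the plan's whole expected effect. Criteria 14 to 16 and 23 already screen out much bladder and median-lobe pathology, so the lower rates are more plausible.

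**Power if these men stay in ITT.** Let c be the control improvement (assumed 2 to 4 points) and f the share of excluded men whose IPSS is set to baseline under the medication rule in SAP I.G.a, with no controls set to baseline. Then effect = (1 - p)(c + 4) + p(1 - f)c - c. With f = 0 this is 4(1 - p): 3.92, 3.80 and 3.60. With f = 1, c = 4 and p = 10% it is 0.9 × 8 - 4 = 3.2.

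| Excluded | 113:57, f = 0 | 113:57, f = 1 | 100:50, f = 0 | 100:50, f = 1 |
|---|---|---|---|---|
| none | 91.5% | 91.5% | 87.7% | 87.7% |
| 2% | 90.4% | 89.8-89.2% | 86.4% | 85.7-85.0% |
| 5% | 88.6% | 86.9-85.0% | 84.3% | 82.3-80.2% |
| 10% | 85.0% | 80.8-75.9% | 80.2% | 75.6-70.4% |

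For month 12 with n = 113 and every excluded man at zero change, the mean is 4(1 - p) against the 1-point bound. Power falls from 99.0% to 98.7%, 98.0% or 96.1%.

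All figures hold the SD at 7.35 and use t-tests rather than the planned covariate-adjusted model, so they are approximations.

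**The case against.** The best defence is that the Note is a prespecified, openly stated exception: a modified ITT under the wrong name, with every exclusion to be reported. That limits post hoc choice. It does not restore comparability when only one arm can lose subjects, and no all-randomized analysis is planned beside it.

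The second objection is size. At 2% to 5% excluded and a gap of 2 points, the bias is at most 0.10 points against a planned effect of 4, and the error rate barely moves. This stands, and the comparison changes only if at least one exclusion occurs.

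Third, deleting the Note would by itself hardly change the primary estimate, because a man with only a baseline value contributes no change value to the repeated-measures model. This also stands, so the fix must include follow-up data. Deletion still matters without follow-up, because it brings these men within reach of the zero-change sensitivity analysis.

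Fourth, the promised reporting of exclusions is worded as a non-exhaustive list, so outcomes and adverse events are not ruled out. They are not promised either. Finally, the SAP says a more detailed version will be written before unblinding. That is a natural place for the correction, but it does not commit to one.

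**Conclusion.** The concern holds. As written, the primary analysis set contradicts its own definition and allows a one-arm exclusion after assignment, which no planned analysis undoes. Confidence is high on that structural point. It rests on the inference that cystoscopy at implantation follows randomization, and on the absence of any described cystoscopy in the control arm.

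Direction and size are not established. The effect is small at low exclusion rates; in the most adverse case tabulated, the false iTIND-win rate roughly doubles, from 2.5% to 5.1%. The need to correct this comes from the contradiction in the set that carries all formal testing, not from a demonstrated bias.

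**What to change.** 1. Delete the Note as it applies to ITT and Safety, and analyse every randomized subject in the assigned arm.
2. After an abandoned implantation, keep collecting IPSS at the scheduled visits and the four secondary measures at month 3.
3. Let the planned repeated-measures model handle missing IPSS in the primary analysis, and name these men in the existing zero-change sensitivity analysis. The general MNAR definition in SAP I.G.b.i could already cover them, so this is a clarification.
4. Reconcile this with the medication rule in SAP I.G.a, which sets IPSS to baseline once an alpha blocker or 5-ARI is started after study treatment begins. Criterion 27 excludes "Subjects who are actively taking medications that affects urination and BPH symptoms not completing the required washout period", so an excluded man who restarts such a drug could have his observed IPSS overwritten. State, for analysis purposes, whether an abandoned implantation counts as starting study treatment. Add a sensitivity analysis that uses these men's observed IPSS. This step is secondary to the others.
5. Define the Safety set to include everyone in whom the implantation procedure was started, cystoscopy included.
6. Report the analysis that omits the intra-operatively excluded men as a sensitivity analysis only.

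The cost is SAP wording, follow-up of a few men and some power. At 5% excluded and 113:57, month-3 power falls by about 3 points in the favourable case (91.5% to 88.6%) and by up to 6.5 points if all excluded men are set to baseline (to 85.0%). The month-12 endpoint loses about 1 point.
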